## **10.6. Sleep quality assessment**

Quality, duration and fragmentation of sleep will be assessed subjectively (using the Pittsburgh Sleep Quality Index (PSQI), and a daily sleep diary) and objectively (by actigraphy) in participants.

The PSQI is a validated 19 item questionnaire that holistically assesses sleep quality and sleep duration. The sleep diary will record time of going to bed and waking, plus time of, and reason for any nocturnal awakenings.

An Actiwatch (Philips Respironics, Bend, Oregon, USA) worn on the non-dominant wrist will provide objective measures of sleep and wakefulness based on motor activity - a low cost, non-invasive and objective method for evaluating sleep in free-living participants. Actiwatches will record time in bed and actual sleep time, as well as changes in sleep quality from measures of sleep maintenance, sleep efficiency, sleep latency, fragmentation index, total nocturnal activity, and percentage moving time. Light exposure will be measured by the Actiwatch's photovoltaic sensor.

## **11. Assessing and Reporting of Adverse Events**

### **11.1. Definitions**

#### **11.1.1. Reportable Adverse Events**

A reportable Adverse Event is any untoward medical occurrence that meets criteria for a serious adverse event or any unanticipated medical occurrence in a study subject that is study or device-related. Device deficiencies that could have led to a serious adverse device effect will also be reported.

#### **11.1.2. Adverse Events**

An adverse event (AE) is any untoward medical occurrence, unintended disease or injury, or untoward clinical signs (including abnormal laboratory findings) in a subject who has received an investigational device, whether or not related to the investigational medical device. This definition includes events related to the device under investigation or the comparator or to the study procedures

The following anticipated adverse events will not be recorded:

- Non clinically significant skin reactions as judged by investigator
- Pre-existing medical conditions

- New illnesses or conditions not requiring concomitant medication or medical intervention/procedures
- Non severe hypoglycaemia
- Hyperglycaemia without significant ketonaemia (>0.6mmol/l)

### **11.1.3. Adverse Device Effect**

An Adverse Device Effect (ADE) is an adverse event related to the use of an investigational medical device. This includes adverse events resulting from insufficient or inadequate instructions for use, deployment, implantation, installation, or operation, or any malfunction of the investigational medical device. This definition also includes any event resulting from use error or from intentional misuse of the device under investigation.

### **11.1.4. Serious Adverse Event**

A serious adverse event (SAE) is an adverse event that:

- Led to a death
- Led to a serious deterioration in the health of the subject, that either resulted in:
  - a life threatening illness or injury
  - a permanent impairment of a body structure or function
  - in-patient hospitalisation or prolonged hospitalization
  - medical or surgical intervention to prevent life-threatening illness or injury or permanent impairment to a body structure or a body function
- Led to foetal distress, foetal death or a congenital abnormality or birth defect

A planned hospitalisation for pre-existing condition, or a procedure required by the study protocol, without a serious deterioration in health, is not considered to be a serious adverse event.

More than one of the above criteria can be applicable to one event. Life-threatening in the definition of a serious adverse event or serious adverse reaction refers to an event in which the subject was at risk of death at the time of the event; it does not refer to an event which hypothetically might have caused death if it were more severe. Medical judgement should be exercised in deciding whether an adverse event or reaction is serious in other situations.

Important adverse events or reactions that are not immediately life-threatening or do not result in death or hospitalisation but may jeopardise the subject or may require

intervention to prevent one of the other outcomes listed in the definition above, should also be considered serious.

The following serious adverse events, should they occur, will be classified as anticipated:

- Severe hypoglycaemia
- DKA

### **11.1.5. Serious Adverse Device Effect**

A Serious Adverse Device Effect (SADE) is an adverse device effect that has resulted in any of the consequences characteristic of a serious adverse event.

### **11.1.6. Unanticipated Serious Adverse Device Effect**

An Unanticipated Serious Adverse Device Effect (USADE) is a serious adverse device effect which by its nature, incidence, severity or outcome has not been identified in the current version of the protocol.

This includes unanticipated procedure related serious adverse events; that is, serious adverse events occurring during the study procedure that are unrelated to any malfunction or misuse of the investigational medical device.

An Anticipated Serious Adverse Device Effect (ASADE) is a serious adverse device effect which by its nature, incidence, severity or outcome has been identified in the current protocol.

### **11.1.7. Device Deficiencies**

A device deficiency is an inadequacy of a medical device with respect to its identity, quality, durability, reliability, safety or performance. A device deficiency may lead to an Adverse Device Effect or Serious Adverse Device Effect. The following anticipated device deficiencies and device-related issues will not be recorded:

- Infusion set occlusion/leakage not leading to ketonaemia
- Sensor failure due to miscalibration/detachment
- Premature interruption of sensor-life
- Battery lifespan deficiency due to inadequate charging or extensive wireless communication
- CAD error messages not needing system replacement

- Intermittent device communication failure not leading to system replacement

### 11.1.8. Adverse Event Intensity

Intensity	Definition
Mild	Patient is aware of signs and symptoms but they are easily tolerated.
Moderate	Signs / symptoms cause sufficient discomfort to interfere with usual activities.
Severe	Patient is incapable of working or performing usual activities.

NB. The term “severe” is often used to describe the intensity (severity) of a specific event. This is not the same as ‘serious’, which is based on patient/event outcome or action criteria (see definition 11.1.4). For example, itching for several days may be rated as severe, but may not be clinically serious.

### 11.1.9. Adverse Event Causality

Intensity	Definition
Not assessable	A report suggesting an adverse event, which cannot be judged because information is insufficient or contradictory, and which cannot be supplemented or verified.
Unlikely	A clinical event, including laboratory test abnormality, with a temporal relationship, which makes a causal relationship improbable, and in which other drugs/treatments, chemicals or underlying disease(s) provide plausible explanations.
Possible	A clinical event, including laboratory test abnormality, with a reasonable time sequence to administration of the treatment/use of investigational treatment/device, but which also could be explained by concomitant diseases or other drugs/treatments or chemicals.

Probable	A clinical event, including laboratory test abnormality, with a reasonable time sequence to administration of the treatment/use of medical method/device, unlikely to be attributable to concomitant disease(s) or other drugs/treatments or chemicals, and which follows a clinically reasonable response on withdrawal (dechallenge). Rechallenge information is not required to fulfil this definition.
Certain	A clinical event, including laboratory test abnormality, occurring in a plausible time relationship to study treatment/use of medical method/device and which cannot be explained by concomitant disease(s), other drugs/treatments or chemicals. The response to withdrawal of the treatment (dechallenge) should be clinically plausible. The event must be unambiguous, either pharmacologically or as phenomenon, using satisfactory rechallenge procedures if necessary.

(Reference: WHO-UMC Causality Categories)

## **11.2. Recording and Reporting of Adverse Events, Serious Adverse Events and Device Deficiencies**

### **11.2.1. Monitoring Period of Adverse Events**

The period during which adverse events will be reported is defined as the period from the beginning of the study (obtaining informed consent) until 3 weeks after the end of the second intervention. Adverse events that continue after the subject's discontinuation or completion of the study will be followed until their medical outcome is determined or until no further change in the condition is expected. The follow up of AEs may therefore extend after the end of the clinical investigation; however no new AEs will be reported after the trial reporting period.

### **11.2.2. Recording and reporting of Adverse Events**

Throughout the course of the study, all efforts will be made to remain alert to possible adverse events or untoward findings. The first concern will be the safety of the subject, and appropriate medical intervention will be taken. The investigator will elicit reports of adverse events from the subject at each visit and complete adverse event forms. All AEs, including those the subject reports spontaneously, those the investigators

observe, and those the subject reports in response to questions will be recorded on paper or electronic AE forms at each site within seven days of discovering the event.

The study investigator will assess the relationship of any adverse event to be device-related or unrelated by determining if there is a reasonable possibility that the adverse event may have been caused by the study device or study procedures. The individual investigator at each site will be responsible for managing all adverse events according to local protocols, and decide if reporting is required.

### **11.2.3. Severe Hypoglycaemia**

Severe hypoglycaemia will be defined as an event requiring assistance of another person to actively administer carbohydrate, glucagon, or other resuscitative actions. These episodes may be associated with sufficient neuroglycopenia to induce seizure or coma. If plasma glucose measurements are not available during such an event, neurological recovery attributable to the restoration of plasma glucose to normal is considered sufficient evidence that the event was induced by a low plasma glucose concentration.

Severe hypoglycaemia will be regarded as a foreseeable serious adverse event and a serious adverse event form will be completed. Non-severe hypoglycaemia will not be reported or considered an adverse event.

### **11.2.4. Hyperglycaemia, Ketonaemia and Diabetic Ketoacidosis**

Diabetic Ketoacidosis (DKA) is defined as: hyperglycemia (blood glucose >250 mg/dl or >13.9 mmol/l) with low serum bicarbonate (<15 mEq/l) and/or low pH (<7.24), anion gap (> 12) and either ketonemia or ketonuria and requiring treatment within a health-care facility (American Diabetes Association Workgroup on Hypoglycemia, Diabetes Care 28:1245-1249, 2005).

DKA will be regarded as a foreseeable serious adverse event and a severe adverse event form will be completed.

Severe hyperglycaemic events (fingerprick glucose >300 mg/dl/16.7mmol/l and blood ketones >0.6mmol/l) will be recorded as Adverse Events. Non-severe hyperglycaemia events will not be reported or considered as adverse events.

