Consistency of treatment effect across sites will be investigated by testing for interaction between study intervention and study site.

Severe hypoglycaemic events and ketone-positive hyperglycaemia will be tabulated in each treatment group, which will be compared (if enough events) using repeated measures logistic regression adjusting for period and whether the subject has ever had a prior event. We will also apply a repeated measures regression model as for the primary analysis to assess treatment differences in absolute terms.

Safety data including severe hypoglycaemia events and ketone-positive hyperglycaemia will be tabulated for all subjects, including drop-outs and withdrawals, irrespective of whether CGM data are available and irrespective of whether closed-loop was operational.

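### Protocol 11.1.2 and 11.2.4 disagree on whether ketotic hyperglycaemia at or below 16.7 mmol/l, short of DKA or a serious adverse event, is recorded as an adverse event

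*Protocol*

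**What the plan says.** Protocol 11.1.2 defines an adverse event broadly, as "any untoward medical occurrence, unintended disease or injury, or untoward clinical signs (including abnormal laboratory findings"). It then lists anticipated events that are not recorded. The hyperglycaemia item in that list is "Hyperglycaemia without significant ketonaemia (>0.6mmol/l"), with no glucose cut-off.

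Protocol 11.2.4 sets a narrower rule: "Severe hyperglycaemic events (fingerprick glucose >300 mg/dl/16.7mmol/l and blood ketones >0.6mmol/l) will be recorded as Adverse Events". The next sentence is "Non-severe hyperglycaemia events will not be reported or considered as adverse events". The same section keeps DKA, starting from "hyperglycemia (blood glucose >250 mg/dl or >13.9 mmol/l"), together with low bicarbonate and/or low pH, an anion gap, ketones and treatment in a health-care facility. It says "DKA will be regarded as a foreseeable serious adverse event".

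On analysis, Protocol 14.5 says "Severe hypoglycaemic events and ketone-positive hyperglycaemia will be tabulated in each treatment group", with a comparison if there are enough events. No glucose condition is attached there. SAP 8.3 does not list ketone-positive hyperglycaemia, but it does tabulate adverse events per subject by treatment group. SAP 8.1 defines DKA from glucose above 11 mmol/l with pH below 7.3 or bicarbonate below 15 mmol/l, plus ketones. That is wider than the protocol's definition.

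**The concern.** Take a participant at home with glucose 15.0 mmol/l and ketones 2.0 mmol/l, no acidosis and no hospital care. The hyperglycaemia item in 11.1.2 does not exempt this event. Under 11.2.4 it is not severe, so it is neither reported nor considered an adverse event. No section ranks the two rules, and 11.2.2 leaves each site investigator to decide whether reporting is required. Two sites could treat the same event differently, and both could point to the protocol.

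Ketosis is a safety matter of direct interest in a trial of automated insulin delivery. An event that was never put on a form cannot be reliably recovered at analysis. The 14.5 tabulation would then mean different things at different sites, and the adverse event totals in the SAP would inherit the same ambiguity.

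**Working it through.** There is no stated figure to reproduce; the check compares recording rules.

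**Units.** 300 / 18.016 = 16.65 and 250 / 18.016 = 13.88 mmol/l, so the protocol's paired thresholds agree after rounding.

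**Rules as coded** (G = glucose, K = ketones, mmol/l):
- 11.1.2, hyperglycaemia item: recorded unless K ≤ 0.6.
- 11.2.4: recorded if (G > 16.7 and K > 0.6), or if protocol DKA (G > 13.9 with bicarbonate < 15 and/or pH < 7.24; the anion gap, ketone and facility-treatment conditions taken as met).
- SAP 8.1 DKA: G > 11, pH < 7.3 or bicarbonate < 15, ketones present.

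| G | K | pH / bicarbonate | 11.1.2 | 11.2.4 | SAP DKA |
|---|---|---|---|---|---|
| 18 | 0.4 | 7.40 / 24 | no | no | no |
| 18 | 1.5 | 7.40 / 24 | yes | yes | no |
| 15 | 1.5 | 7.40 / 24 | yes | **no** | no |
| 15 | 1.5 | 7.28 / 17 | yes | **no** | yes |
| 15 | 1.5 | 7.20 / 12 | yes | yes (DKA) | yes |
| 13.5 | 1.5 | 7.20 / 12 | yes | **no** | yes |
| 12 | 1.5 | 7.40 / 24 | yes | **no** | no |

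The rules agree whenever K ≤ 0.6, and whenever K > 0.6 with G > 16.7. They disagree for K > 0.6 with G ≤ 16.7, except for protocol DKA. Some SAP-defined DKA lies in the disputed region (rows 4 and 6), unless it qualifies as a serious adverse event under 11.1.4, for example through hospitalisation.

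**Could this distort the comparison of arms?** Let s be the share of ketotic events at or below 16.7 mmol/l and c the fraction of those that are recorded. With equal true rates, the observed ratio (closed loop / control) is

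R = (1 − s_CL + s_CL·c_CL) / (1 − s_C + s_C·c_C).

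The documents give neither s nor c, so every value below is assumed.
- Same s and same c in both arms: R = 1.00 for any s.
- Same s, full recording in closed loop and half in control: R = 1 / (1 − s/2) = 1.11, 1.25, 1.43 for s = 0.2, 0.4, 0.6. If control records none: R = 1 / (1 − s) = 1.25, 1.67, 2.50. Swapping the arms inverts these.
- Nothing recorded below the cut in either arm, but s differs: R = (1 − s_CL) / (1 − s_C). Assume glucose at ketotic events is normal with SD 4 and a gap of 0.6 mmol/l between arms. The gap is borrowed from the overall mean glucose of 9.3 versus 8.7 in the 12-week adult study in Protocol 4.9. Means of 17.5 and 16.9 put 57.9% and 52.0% above 16.7, so R = 0.520 / 0.579 = 0.90. Means of 20 and 19.4 give 0.94; 22 and 21.4 give 0.97. With control at 17.5, no gap gives 1.00 and a gap of 1.2 gives 0.79.

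**The case against.** The strongest reply is that this is a wording mismatch with little consequence. Its parts fare differently.

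- **The stated outcome is safe.** The synopsis, 10.2 and 11.2.4 all define severe hyperglycaemia as above 16.7 mmol/l with ketones above 0.6 mmol/l. This stands: a reader might infer that this outcome depends on which section a site follows, but it does not.
- **The phrase in 14.5 may be shorthand for that outcome.** Possible, but the protocol does not say so, and the SAP does not settle it.
- **Other routes catch the events.** DKA from above 13.9 mmol/l is kept, as is anything meeting 11.1.4. Section 11.1.7 exempts only infusion-set occlusion or leakage that does not lead to ketonaemia, and 11.2.6 documents device deficiencies. An occlusion with ketosis therefore leaves a device record. This stands in part: that record is not an adverse event and does not enter the adverse event counts.
- **11.1.2 also exempts new conditions needing no medication or medical intervention.** This might cover some home-managed events. It adds to the ambiguity rather than resolving it, because the list deals with hyperglycaemia in its own item.
- **DKA starts at a lower glucose than severe hyperglycaemia.** A reader might infer that the grading is out of order. The documents do not support that: the DKA glucose value is one entry condition among several, not a severity grade.
- **Wider recording brings its own problem.** The documents give no rule for when ketones are tested, so counts at lower glucose would depend on ad hoc testing in an open-label trial. This stands as a limitation of the fix.

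**Conclusion.** The inconsistency is real and limited to hyperglycaemia with ketones above 0.6 mmol/l and glucose at or below 16.7 mmol/l that meets neither the DKA nor the serious adverse event criteria. It affects the 14.5 tabulation, the SAP adverse event counts and possibly some SAP-defined DKA. Its size in events is unknown, and with about 36 randomised participants the events may be few. The main loss is incomplete or site-dependent safety records rather than a wrong p-value.

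Two stronger readings go too far. A reader might infer that 11.2.4 drops every event at or below 16.7 mmol/l; it does not, because DKA and serious adverse events are kept. A reader might also infer that the arm counts are biased in favour of closed loop. That requires either recording that differs by arm, or a different glucose distribution at ketotic events together with incomplete recording below the cut. Open-label conduct and investigator discretion make the first possible, and a glucose-lowering treatment makes the second plausible. Neither is established. The ratio of 0.90, and the 42% and 48% of events below the cut behind it, follow from an assumed mean and SD with no source. The 0.6 mmol/l gap is an overall mean difference from an earlier study in adults of mean age 40, and nothing links it to ketotic episodes. Amending the plan is still justified, because events not recorded cannot be reliably reconstructed later.

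**What to change.** Reconcile Protocol 11.1.2, 11.2.4 and 14.5 with SAP 8.1 and 8.3 to a single recording rule, applied the same way in both periods and at all sites:

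1. Record every hyperglycaemic event found to have ketones above 0.6 mmol/l as an adverse event, with its glucose and ketone values.
2. Tabulate all such events by treatment group as the ketone-positive hyperglycaemia of 14.5, and add that line to SAP 8.3.
3. Report the subset above 16.7 mmol/l as the severe hyperglycaemia outcome, unchanged.
4. Reconcile the protocol and SAP definitions of DKA, so that no event counted as DKA in the analysis can be classed as non-severe at the site. Which threshold is right is not judged here.

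The SAP gives the study stage as active. If the rule changes mid-trial, earlier events should be sought in source records, and the report should state from when the rule applied.

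The cost is a sentence in 11.2.4, matching edits in the other sections, one extra table row and a few more adverse event forms. Counts at lower glucose will still depend on when ketones happen to be tested, and the report should say so. The change concerns data capture only and sets no clinical management rule.

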## **11.2.5. Reporting of Serious Adverse Events and Serious Adverse Device Effects**

When reporting adverse events, all pertinent data protection legislation must be adhered to.

The serious adverse event report should contain the following information\*:

1. Study identifier (EudraCT number if applicable)
2. Participant's unique study number
3. Date of birth
4. Event description
5. Start date of event
6. Laboratory tests used and medical interventions used to treat the SAE
7. Planned actions relating to the event, including whether the study device was discontinued
8. Statement on the patient's current state of health
9. Reason for seriousness (i.e. death, life threatening, hospitalisation, disability/incapacity or other)
10. Evaluation of causality (including grade of relatedness) with the following (more than one may apply):
  - a. the investigational treatment/medical device
  - b. the clinical study/a study specific procedure
  - c. other: e. g. concomitant treatment, underlying disease
11. Reporter's name, date and signature

\*In the case of incomplete information at the time of initial reporting, all appropriate information should be provided as soon as this becomes available.

The relationship of the SAE to the investigational treatment / medical device should be assessed by the investigator at site, as should the anticipated or unanticipated nature of any SAEs and SADEs.

All SAEs whether or not deemed investigational method/device related and whether anticipated or unanticipated must be reported to the Sponsor by email or fax within 24 hours (one working day) of the Investigator learning of its occurrence.

**UK specific reporting instructions:**

SAEs should be reported to:

[name]

Cambridge University Hospitals

NHS Foundation Trust

[name]

[name], UK

[contact]

[contact]

E-mail: [r&[contact]](mailto:r&[contact])

A written report must follow within five working days and is to include a full description of the event and sequelae, in the format detailed on the Serious Adverse Event reporting form. If applicable, the Sponsor will notify the competent authority of all Serious Adverse Events in line with pertinent legal requirements.

The Investigator will notify the Research Ethics Committee (REC) in UK of all Serious Adverse Events in line with pertinent legal requirements. The Investigator will inform the Sponsor about all reports sent to the reporting organisation including follow-up information and answers by the reporting organisation. The local investigator is responsible for informing other site principal investigators and the CI of all SAEs.

The regulatory authority (MHRA will be notified of all SAEs as soon as possible within ten days of the event occurring during the study. The main REC will be notified of all unexpected and related SAEs within 15 days of the occurrence of the event.

